APACHE	Acute Physiology and Chronic Health Evaluation
VFD	Ventilator-free days
LAR	Legally authorized representative

Protocol Synopsis

Study Title	Effect of Esophageal Pressure Measurement to Determine Optimal Positive End-expiratory Pressure Compared to Usual Care in Obese Patients Receiving Mechanical Ventilation
Funder	Departmental funds
Study Rationale	
The use of positive end-expiratory pressure (PEEP) in mechanical ventilation is important to reduce the collapse of alveoli between breaths. This atelectasis increases the patient's work of breathing and impairs oxygenation. In addition, atelectrauma can lead to ventilator-induced lung injury through repetitive shear injury. There is a patient-specific response to PEEP titration, but PEEP titration is frequently not guided by individual patient data. Obese patients have less compliant chest walls, which increases the apparent airway pressure required to provide mechanical ventilation. Titration of PEEP to levels high enough to prevent atelectasis and improve chest wall compliance in these patients yields apparently unsafe pressures. Yet these pressures are not likely transmitted to the alveoli. In order to evaluate the pressure transmitted to the alveoli, one should consider the pleural pressure. Direct measurement of the pleural pressure is highly invasive and poses risk to the patient. However, estimation of the pleural pressure using an esophageal pressure monitor is significantly less invasive and provides an acceptable alternative for estimation of transpulmonary pressure (Ptp). Preliminary work by members of the research group evaluated time to wean from mechanical ventilation in obese patients requiring tracheostomy. Use of Ptp to guide PEEP choice resulted in a significant reduction in the median time to wean, from 14 days to 3.5 days ($p=0.012$). We propose that esophageal pressure measurement can guide optimal PEEP selection in obese patients who require mechanical ventilation and reduce their time on the ventilator.

Study Objective(s)	To evaluate whether esophageal pressure measurement to determine optimal PEEP in obese patients receiving mechanical ventilation can reduce time on the ventilator when compared to usual care.
Study Design	Randomized-controlled clinical trial. Patients will be enrolled within 4 days of mechanical ventilation and randomized 1:1 to titration of PEEP based on esophageal balloon pressures or based on the "High PEEP" ARDSnet PEEP/FiO ₂ table. All patients will have esophageal balloons placed with baseline measurement of Ptp. Patients randomized to the intervention arm will then undergo titration of PEEP based on Ptp measurements to achieve "Optimal PEEP," defined as end expiratory Ptp of 0 to +2 cm H ₂ O.

Subject Population key criteria for Inclusion and Exclusion:	
Inclusion Criteria: Obese adults (BMI ≥ 40) admitted to the medical ICU at UNC Hospitals or Vidant Medical Center at ECU with acute respiratory failure requiring mechanical ventilation.
 
Exclusion Criteria:
 
 1. Refusal to give consent by subject or LAR 2. Abdominal compartment syndrome 3. Chest tube for pneumothorax 4. Having been on a ventilator for >4 days 5. Suspicion of or known intracranial hypertension 6. Anticipated extubation within 24 hours 7. Chronic ventilator dependence 8. Condition that precludes placement of an esophageal balloon (esophageal or nasopharyngeal pathology preventing insertion of the esophageal balloon catheter, severe thrombocytopenia, or coagulopathy) 9. Incarceration 10. Not expected to survive >48 hours 11. Unable to obtain consent from subject or LAR 12. Unable to obtain consent due to a language barrier
Number Of Subjects	76 patients
Study Duration	Each subject's participation will last for up to 28 days. The entire study is expected to last about 12-24 months.
Study Phases	
(1) Screening: Screening for eligibility and obtaining consent for enrollment.
 
(2) Pre-Intervention: Esophageal balloon placed and baseline data collected.
 
(3) Intervention: PEEP titrated to achieve Optimal PEEP in the intervention group. Ptp Measurements will be obtained daily and adjustments to PEEP will occur daily.
 
(4) Subject Completion/Withdrawal: Study will conclude for each patient at 28 days after enrollment or hospital discharge.

Efficacy Evaluations	Primary evaluation measurements that will be used to assess the efficacy of the intervention are ventilator free days at day 28. Differences between control and intervention groups will be attributed to differences in PEEP management.
Safety Evaluations	Periodic review will be performed by the NC TraCS DSMB. They will review aggregate safety data after 25, 50, and 75% enrollment to ensure there are not safety differences between the groups in hypotension requiring vasopressors and development of pneumothorax. All patients will have

continuous monitoring of HR, BP, and oxygenation per ICU protocol to monitor patient safety.

Statistical And Analytic Plan

This is a randomized, controlled trial to evaluate the effect of using Optimal PEEP based on an esophageal balloon measurement on duration of mechanical ventilation. We hypothesize that using Ptp to identify optimal PEEP will reduce time on the ventilator and therefore increase the ventilator free days at day 28. The primary outcome is the number of ventilator-free days, defined as the number of days alive and ventilator-free by day 28. Differences between the two groups in the primary outcome will be analyzed using independent t-tests and a linear regression model adjusting for BMI, abdominal girth, and Ptp.

DATA AND SAFETY MONITORING PLAN

The PI will be responsible for maintaining patient data and ensuring accuracy of the data collected. All patient data will be collected using REDCap through the NC TraCS system. REDCap allows for immediate data validation and range setting to reduce the likelihood of erroneous data entry. Data created for analysis will be de-identified and secured on a password protected UNC School of Medicine network hard drive. All investigators will be trained on completing the electronic case report form.

Patient safety will be monitored with continuous cardiovascular monitoring by the critical care team. Subject stopping rules will be in place to end the study intervention, including refractory hypotension, development of pneumothorax, or changes in oxygenation or hemodynamics that the primary team feels may be related to changes in PEEP.

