4.4 Participant Completion/ Withdrawal

Participants will complete the study at the time of death or the conclusion of 28 days, whichever occurs first.

Early completion of the trial for each participant will occur if any of the following outcomes are met:

- a. Patient or family withdraw consent for the study
- b. The clinical team feels that the patient no longer meets appropriateness for the study
- c. Patient develops an adverse effect felt possibly related to the intervention (refractory hypotension, nasopharyngeal bleeding, pneumothorax, etc)

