- 5) Other signs of respiratory distress (distress = 2 or more)
- 6) HR > 140
- 7) Marked accessory muscle use
- 8) Abdominal paradox (belly breathing)
- 9) Diaphoresis

Failure of an SBT will be determined by the bedside RT based on current policy (PolicyStat ID: 4745433). If a patient fails an SBT, they will be returned to their previous ventilator settings until the next daily assessment. If the patient tolerates a 30-minute SBT, they will be returned to their previous ventilator settings for 60 minutes, then extubated to an appropriate oxygen delivery device. Ventilator settings during the SBT and extubation procedures will vary between groups as below. Blinding of the respiratory therapist determining eligibility for SBT to treatment arm will not be possible because of the differences between SBT protocols. However, the study team will make no determinations of readiness for extubation. If a member of the study team is on service during the time of potential enrollment, these patients will be excluded to avoid bias.

SBT and Extubation Procedure for Intervention Group

Patients in the Intervention group will undergo an SBT regardless of their PEEP level. The PEEP that generates a Ptp of 0 will be considered their optimal PEEP, and this will not be lowered for the SBT. The Intervention Group SBT will consist of a trial of a pressure support of 5 cm H₂O and Optimal PEEP.

SBT and Extubation Procedure for Control Group

Patients in the Control group will undergo an SBT **when they reach a PEEP \leq 8 cm H₂O**. This is the current standard of care based on the SBT protocol at UNC Hospitals. SBT and extubation prior to meeting these criteria will be based on primary medical team's discretion and will be recorded for analysis and safety tracking.

Procedures for ventilator weaning after tracheostomy

Any patient who fails to be eligible for extubation or fails extubation will be eligible for tracheostomy per usual unit protocol. The study team will play no part in the decision to proceed with tracheostomy for ventilator weaning. After tracheostomy, it is routine practice to forego SBT and proceed with trials of liberation from the ventilator with oxygen delivered by an aerosol tracheostomy collar ("trach collar trials" or TCT). The same criteria are used to perform a TCT as an SBT above. The two groups will have different approaches to TCT.

TCT Procedure common to both groups

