5.2 Other measurements

Variable	Source	How Measured	Baseline	Daily	Completion
Outcomes					
Ventilator free days at day 28 (Primary outcome)	EMR	Days alive and free of the ventilator			X
Reintubation	EMR	Intubated within 72 hours of extubation		X	X
ICU Length of Stay	EMR	Days			X
Hospital Length of Stay	EMR	Days			X
Tracheostomy	EMR	Y/N			X
Extubation prior to meeting established criteria	EMR	Y/N			X
Highest RASS	EMR	-5 to +4 (single highest value used)	X	X	
Lowest RASS	EMR	-5 to +4 (single lowest value used)	X	X	
Exposures					
Esophageal pressure (Pes)	Ventilator	cm H ₂ O	X	X	
Airway pressure (Paw)	Ventilator	cm H ₂ O	X	X	
Transpulmonary pressure (Ptp) (inspiratory and expiratory)	Ventilator	cm H ₂ O	X	X	
PEEP	Ventilator	cm H ₂ O	X	X	
Opioids	EMR	Continuous, bolus sch, bolus prn, oral sch, oral prn	X	X	
Propofol	EMR	Y/N	X	X	
Dexmedetomidine	EMR	Y/N	X	X	
Benzodiazepines	EMR	Continuous, bolus sch, bolus prn, oral sch, oral prn	X	X	
Antipsychotics	EMR	Sched, PRN	X	X	
Neuromuscular blockade	EMR	Y/N	X	X	
Corticosteroid use	EMR	Y/N	X	X	
Fluid Balance	EMR	Net fluid balance prior to extubation		X	
Safety Measures					
Vasopressor requirement	EMR	norepinephrine equivalents(9)	X	X	
Pneumothorax	EMR	Y/N	X	X	
Other Variables of Interest					
Age	EMR	Years	X		
Race/Ethnicity					
BMI	EMR	kg/m ²	X		
Partial Pressure of Oxygen (PaO ₂)	EMR	mmHg	X	X	
Oxygen Saturation (SpO ₂)	EMR	%	X	X	

PaO ₂ /FiO ₂ ratio	Calculated	Number	X	X	
SpO ₂ /FiO ₂ ratio	Calculated	Number	X	X	
Charlson Comorbidities	EMR	Y/N	X		
Waist circumference	EMR	cm	X		
CAM-ICU	EMR	Positive/Negative	X	X	
SOFA	EMR	Calculated	X		
COVID (y/n)	EMR	Y/N	X		

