6 STATISTICAL CONSIDERATION

6.1 Primary Endpoint

The primary outcome is the number of ventilator-free days (VFD), defined as the number of days alive and ventilator-free by day 28. The assessment of the primary outcome will be conducted by a study team member after subject completion in the study. In order to minimize potential bias, this team member will be blinded to treatment arm assignment.

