6.3 Sample Size and Power

We utilized preliminary data from earlier studies of mechanical ventilation in the obese to establish a baseline. With a mean duration of mechanical ventilation of 7 days with a standard deviation of 2.9 days, we expect the control group to have 21 ventilator free days. We estimate that we could reasonably see an effect in the intervention group that reduces the duration of mechanical ventilation by 3 days. With a power of 80% and alpha=0.05, we would need 16 patients per group, for a total of 32 patients. Would the effect be only a reduction of mechanical ventilation by 2 days, we would need 34 patients in each group for a total of 68 patients. Because the population in our study would be expected to have a lower mean duration of mechanical

ventilation, we anticipate we may find a smaller effect size. Including a possible 10% dropout, we will target a sample size of 76 (38 per group) to safely achieve our goals.

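### The ventilator-free-day count keeps the days before a post-extubation death, so the primary endpoint can under-penalise excess deaths off the ventilator

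*Combined protocol and SAP*

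**What the plan says.** The synopsis (Statistical And Analytic Plan) reads: "The primary outcome is the number of ventilator-free days, defined as the number of days alive and ventilator-free by day 28". Section 6.1 has the same definition: "The primary outcome is the number of ventilator-free days (VFD), defined as the number of days alive and ventilator-free by day 28". The 5.2 table gives the measurement as "Days alive and free of the ventilator". The three statements agree. None sets a separate score for patients who die.

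Section 6.2 compares the arms on this count with a two-sided t-test. Section 6.3 plans on a ventilation time, "With a mean duration of mechanical ventilation of 7 days with a standard deviation of 2.9 days", and converts it directly: "we expect the control group to have 21 ventilator free days". That is 28 - 7, with no allowance for deaths.

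Mortality is not among the outcomes in 5.2. Death otherwise appears as an end of participation (3.3, 4.4) and as a suspension trigger in 7.3 that is applied to all enrolled subjects together.

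The arms differ in when a breathing trial is allowed. Section 5.1 says "Patients in the Intervention group will undergo an SBT regardless of their PEEP level", while controls by default wait until PEEP is 8 cm H₂O or less. The readiness and failure criteria are common to both arms.

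**The concern.** Under a literal count, death removes only the days that follow it. A patient who comes off the ventilator and later dies keeps every day in between and can rank above a survivor who was ventilated for longer. An arm designed to reach extubation sooner earns more credited days before each later death.

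If extubation from higher PEEP were followed by more late deaths, the primary comparison would register only part of that harm, and the mean difference could favour the arm with more deaths. No other planned comparison by arm would show it, since mortality is not a listed outcome.

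**Working it through.** **Inputs from 6.3.** Control ventilation 7 days, SD 2.9; reductions of 3 or 2 days; 80% power; alpha 0.05, two-sided (6.2). The exact t-test calculation gives 15.7, so 16 per group, for 3 days, and 33.99, so 34 per group, for 2 days. Then 68/0.9 = 75.6, so 76. The plan's figures reproduce. The final size rests on the 2-day effect, so that effect is used here: 7 vs 5 days, or 21 vs 23 VFD in survivors.

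**Assumed, because the documents do not give them.** Mortality by day 28 and the day of death, D.

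**Single patients, as written (D - day of extubation).**
- Extubated day 3, dead day 27: 27 - 3 = 24, above the planned control mean of 21.
- Extubated day 4, dead day 20: 20 - 4 = 16, equal to a survivor ventilated for 12 days (28 - 12).

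**Difference in means (intervention minus control), all deaths after extubation.** With mortality p₁ (intervention) and p₀ (control):
- As written: [(1 - p₁)·23 + p₁(D - 5)] - [(1 - p₀)·21 + p₀(D - 7)] = 2 - (p₁ - p₀)(28 - D).
- Death = 0: 23(1 - p₁) - 21(1 - p₀).

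| Mortality | As written, D = 10 | D = 14 | D = 20 | D = 24 | Death = 0, any D |
|---|---|---|---|---|---|
| 30% vs 20% | +0.2 | +0.6 | +1.2 | +1.6 | 16.1 - 16.8 = -0.7 |
| 35% vs 20% | -0.7 | -0.1 | +0.8 | +1.4 | 14.95 - 16.8 = -1.85 |

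**Break-even excess mortality.** As written, 2/(28 - D): 11 points at D = 10, 14 at D = 14, 25 at D = 20. With death = 0, 2(1 - p₀)/23: 7.8, 7.0 and 6.1 points at control mortality of 10%, 20% and 30%, whatever the day of death.

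**Deaths on the ventilator.** A patient never off the ventilator scores 0 under both rules. If all deaths in the 30% vs 20% case were of this kind, the as-written difference would also be -0.7.

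**Simulated t-tests.** 4,000 trials, 34 per arm, durations normal with SD 2.9, means 5 vs 7, mortality 30% vs 20%, all deaths after extubation:
- Deaths on days 20 to 28: as written, significant for the intervention in 43% of trials and for control in 0%.
- Deaths spread over days 8 to 28: 9% and 0.3%.
- Death = 0, either timing: about 1% and 5%.

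**Masking that remains with death = 0.** With 4 vs 7 days and mortality 25% vs 20%: 0.75·24 - 0.80·21 = 18.0 - 16.8 = +1.2 for the arm with more deaths.

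**Cost in power.** 38 per arm, 5 vs 7 days, 20% mortality in both arms, half of deaths on the ventilator and the rest spread between extubation and day 28. Moving to death = 0 raises the SD from about 7.4 to about 8.8, and t-test power falls from about 15% to 11%.

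**The case against.** The present rule is complete, computable and consistent, and it does penalise death: every day from death to day 28 is lost. It would be wrong to say that the plan leaves death unscored. Death = 0 is partly a choice of estimand, since it equates a death on day 27 after 24 days off the ventilator with survival for 28 days on it. That stands, but it does not defend an endpoint on which such a patient outscores the planned average control patient.

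A reader might infer that a more lethal strategy will look beneficial. The documents do not support that. They give no mortality, no timing of death, and no evidence that extubation from higher PEEP causes late deaths. Both arms face the same readiness and failure criteria, the study team makes no extubation decisions, and reintubation within 72 hours is recorded.

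A striking reversal can be built on the 3-day effect: with 35% vs 20% mortality and death on day 14, the count gives 3 - 0.15·14 = +0.9, against 0.65·24 - 16.8 = -1.2 with death = 0. At the 2-day effect on which the trial is sized, the same case gives -0.1 as written, so that reversal disappears. Simulating the 3-day case at 38 per arm, with some deaths on the ventilator, the count significantly favours the intervention in only about 5% of trials. The 43% figure above needs all deaths to fall on days 20 to 28.

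The death trigger in 7.3 offers little protection. It is pooled and set at 60% once more than 10 are enrolled, while 30% vs 20% averages 25%.

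**Conclusion.** The concern holds in conditional form. As written, a patient who dies after extubation keeps the earlier ventilator-free days and can outscore a survivor; that follows from the definition alone. Whether the arm comparison is distorted depends on assumed mortality and timing. At the 2-day effect and 30% vs 20% post-extubation mortality, the count favours the intervention for deaths on any day from 10 to 24, while death = 0 favours control. At 35% vs 20% it does so only for the later deaths (-0.7 to +1.4, against about -1.9). Excess deaths on the ventilator are already penalised.

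A reader might also infer that scoring death as 0 cures the problem. It does not: an excess of up to about 6 to 8 points can still be offset by a 2-day gain. Mortality by arm is therefore needed beside the result. The sponsor may already intend death to score 0, but the text does not say so, and an assessor following it would credit the days before death.

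**What to change.** 1. In the synopsis, the 5.2 table and 6.1, score VFD as 0 for any patient who dies by day 28, whenever extubated. For survivors, keep the count to day 28.
2. Keep the present count as a pre-specified sensitivity analysis.
3. Add 28-day mortality by arm to 5.2 and report it beside the VFD result.
4. Reconcile the follow-up statements. The synopsis (Study Phases) and 3.3 allow participation to end at hospital discharge, whereas 4.4 says "Participants will complete the study at the time of death or the conclusion of 28 days, whichever occurs first". Day-28 vital status must be known for every patient.
5. Restate the mean, SD and power in 6.3 with deaths included.

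The cost is wording in three places, ascertainment of vital status after discharge, and about 4 points of t-test power (15% to 11% under the assumptions above). That is about a quarter of the power remaining. Most of the shortfall from 80% arises under either rule, because 6.3 plans without deaths. The changes should be made before outcome data are analysed.

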7.2 Data and Safety Monitoring Plan

All participants will be continuously monitored by critical care nurses under the guidance of critical care physicians per individual ICU protocols.

Stopping rules and procedures

Subject stopping rules will be the development of any of the following after randomization:

- New pneumothorax
 - Pneumothorax is a known risk factor for all patients requiring mechanical ventilation with a case rate of <1% of all mechanically ventilated patients. In previous studies of optimal PEEP determination using esophageal balloon-guided pressure measurement, no pneumothoraces were observed. We believe the study procedures will be safe for both arms, and that the intervention arm will be at lower risk for this outcome. However, development of a pneumothorax will necessitate a chest tube and will invalidate the measurement of pleural pressure. Therefore the study procedures must be stopped.
- Epistaxis requiring intervention
 - In the event of epistaxis requiring packing or intervention, the esophageal balloon will be removed and the study subject's participation in the study will end.
- Hypotension
 - In the event a patient experiences a drop in mean arterial pressure (MAP) below 65 mm Hg or a significant change in vasoactive medication requirement (>10 mcg/min dose of norepinephrine equivalent), that is felt by the clinical ICU team to possibly be related to the intervention, the study subject's PEEP will be dropped by 2 cm H₂O every 5 minutes until the parameter returns to an acceptable range (as determined by the clinical ICU team) or until the PEEP reaches the pre-intervention level. The patient will remain on no higher than this new PEEP for the remainder of the study.

Adverse Event Reporting

All Adverse Events will be documented and graded using CTCAE grading, defined as any patient who develops one of the following (by CTCAE grading):

- grade 3-5 hypotension
- grade 2-5 pneumothorax
- grade 2-5 epistaxis

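### Patients stopped early under 4.4 b/c or the 7.2 epistaxis rule can be closed without a day-28 VFD, because no sentence requires outcome follow-up after a stop and 6.2 disregards missing values

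*Combined protocol and SAP*

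**What the plan says.** The Data and Safety Monitoring Plan in the synopsis describes what a subject stop ends: "Subject stopping rules will be in place to end the study intervention, including refractory hypotension, development of pneumothorax, or changes in oxygenation or hemodynamics". It does not mention outcome follow-up.

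Section 4.4 gives a different consequence: "Early completion of the trial for each participant will occur if any of the following outcomes are met". Three reasons follow. Item a is withdrawal of consent. Item b reads "The clinical team feels that the patient no longer meets appropriateness for the study". Item c reads "Patient develops an adverse effect felt possibly related to the intervention (refractory hypotension, nasopharyngeal bleeding, pneumothorax, etc". All three have the same effect.

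Section 7.2 lists subject stopping rules by event, and they differ from each other:

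- Pneumothorax: "Therefore the study procedures must be stopped".
- Epistaxis needing packing or intervention: the balloon is removed and the subject's "participation in the study will end".
- Hypotension: PEEP is stepped down, then "The patient will remain on no higher than this new PEEP for the remainder of the study". The patient stays in the study.

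On the outcome, 3.1 plans 28 days of follow-up for VFD, 5.2 names the EMR as the source, and 4.2 and 6.1 give the assessment to a blinded team member once the subject has completed. Section 6.2 specifies a two-sided t-test and disregards missing values. Section 6.3 adds a 10% dropout allowance. No section defines an analysis population or says how an early-stopped patient is analysed.

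**The concern.** Ending a patient's treatment and ending a patient's follow-up are separate decisions, and the protocol does not keep them apart. Staff who apply 4.4 b, 4.4 c or the epistaxis rule as written can close the record at the stop. That patient may then have no day-28 VFD and would drop out of the primary comparison without any rule being broken.

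Such losses would not be random. They follow how the patient is doing, and items b and c rest on the judgement of clinicians who know the arm, since 3.1 and 4.2 state that the clinical team cannot be blinded. The primary t-test would then compare only the patients who were not stopped, and the protection of randomization would be weakened for the sake of data that the hospital record probably holds.

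**Working it through.** **1. The same events side by side**

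| Event | Synopsis | 4.4 | 7.2 |
|---|---|---|---|
| Pneumothorax | Intervention ends | Early completion (c) | Study procedures stop; follow-up not mentioned |
| Refractory hypotension | Intervention ends | Early completion (c) | No rule for this term; the hypotension rule lowers and caps PEEP, patient stays in |
| Nasal bleeding | Not listed | Early completion (c) | Participation ends (epistaxis needing intervention) |
| Oxygenation or hemodynamic change, in the primary team's view | Intervention ends | Could fall under b or c | Only hypotension covered |
| Team finds patient no longer appropriate | Not listed as such | Early completion (b) | Not listed |

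The protocol does not define refractory hypotension.

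**2. Does VFD survive a stop?** Section 3.1 sets 28-day follow-up in general terms. Section 6.1 places the assessment after subject completion, but 4.4 makes these stops a form of completion, so 6.1 fits either an assessment of the full 28 days or a record closed at the stop. The EMR source makes collection feasible. None of these sentences requires it. If VFD is not collected, 6.2 removes the patient.

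**3. The plan's own sample size.** Inputs from 6.3: SD 2.9 days, power 80%, alpha 0.05 (two-sided in 6.2).

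- 3-day effect: the t-based calculation gives 15.7 per group, rounded up to the stated 16.
- 2-day effect: 33.99, the stated 34 per group, 68 in total.
- Dropout: 34/0.9 = 37.8, so 38 per group and 76 in total. The allowance is 76 - 68 = 8 patients, for any reason.

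These figures reproduce and are not in dispute.

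**4. Shift from ignored patients.** Let k of the 38 patients in an arm be ignored, each with a VFD D days below the mean M of the other 38 - k. The full-arm mean is M - kD/38. Ignoring the k patients leaves M, so the arm's mean rises by kD/38. The documents give no D. I assume 7, 14 and 21, where 21 is the planned control mean VFD in 6.3.

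| D (assumed) | Shift per ignored patient |
|---|---|
| 7 | 7/38 = 0.18 day |
| 14 | 14/38 = 0.37 day |
| 21 | 21/38 = 0.55 day |

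With the same D in both arms, the shift in the between-arm difference is (k1 - k0) x D/38, where k1 and k0 are the numbers ignored in the intervention and control arms. If k1 = k0, it is zero.

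**5. How many stops?** The only rate given is for pneumothorax, under 1% of ventilated patients (7.2). At 1%, 0.01 x 76 = 0.76 patients in the whole trial. No rate is given for epistaxis, refractory hypotension or team judgement.

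**6. Direction.** Both arms receive the catheter, so both carry the bleeding risk. Controls follow the High PEEP table, so they too may receive high PEEP. For pneumothorax, 7.2 expects that "the intervention arm will be at lower risk for this outcome". Nothing here says which arm would lose more patients.

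**The case against.** The best case for the plan is that VFD will not be missing. It comes from the EMR, is defined to day 28 whatever the stop date, and is determined by a blinded assessor after completion, which can include early completion. Stops may also be few: 7.1 reports no adverse effects in a small randomized trial of balloon-guided PEEP, 7.2 reports no pneumothoraces in earlier balloon-guided studies, and severe thrombocytopenia and coagulopathy are exclusions. This stands as evidence that collection is feasible and the effect may be small. It does not supply the missing instruction, and the 10% dropout allowance suggests that some loss is expected.

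Four stronger readings are tempting and are not supported:

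- **The synopsis and 4.4 flatly contradict each other.** The synopsis does not say that only the intervention ends, and closing a patient's trial also ends the intervention. The texts differ in what they make a stop do. Item 4.4 b is also a general judgement, not a harm stop as such.
- **4.4 c cannot be reconciled with the 7.2 hypotension rule.** Refractory hypotension can be read as a tier beyond hypotension that responds to the step-down. The fault is that this tier is left undefined.
- **The bias could equal the planned effect.** If all 8 allowed dropouts were low-VFD stops split 6/2 with D = 21, the shift would be 4 x 21/38 = 2.21 days, against the 2-day effect in 6.3. That is a worst case, not an estimate: the allowance includes consent withdrawal, and the documents support neither the split nor the D.
- **Keeping everyone raises power from 80.0% (34 per arm) to 84.3% (38 per arm).** This assumes that retained patients fit an SD of 2.9. If 4 of 38 lie D days lower, the variance becomes 2.9² + (4/38)(34/38)D², so the SD is about 3.6, 5.2 or 7.1 for D of 7, 14 or 21. The power gain cannot be claimed together with the bias.

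**Conclusion.** The point holds as a gap with a specific consequence. Rules that close a patient's trial, the lack of any requirement to obtain VFD afterwards, the unstated analysis population and the disregard of missing values together allow condition-related losses from the primary t-test. Direction and net size are unknown. Each ignored patient moves an arm's mean by 0.18 to 0.55 day under the assumed D of 7 to 21. Balanced losses with equal D cancel, and rare stops leave little effect. The calculation assumes 38 per arm and that ignored patients have lower VFD than the rest. The differences in wording are certain. Whether VFD would actually go uncollected cannot be settled from the documents. The plan should still be amended, because the loss is avoidable at almost no cost.

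**What to change.** 1. In 4.4 b, 4.4 c and the 7.2 epistaxis and pneumothorax rules, state that the event ends the study procedures (balloon measurement in either arm, Ptp-guided titration in the intervention arm) but not outcome follow-up. The balloon is still removed for epistaxis.
2. Keep the 7.2 step-down and cap rule for hypotension that responds. State that refractory hypotension ends the intervention, as the synopsis says, also without ending follow-up.
3. State that the blinded assessor determines VFD to day 28 from the EMR for all of these patients, and that among the 4.4 reasons only withdrawal of consent ends data collection.
4. In 6.2, state that all randomized patients with an obtainable VFD are analysed in their randomized arm, and report stops and reasons by arm.

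The cost is a wording amendment to 4.4, 6.2 and 7.2 and one stop-reason field on the case report form. The clinical triggers and the sample size do not change, and no power gain is claimed. VFD after hospital discharge concerns every participant (the synopsis and 3.3 let participation end at discharge) and needs its own sentence; these changes do not settle it.
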